### **Supported by:**

#### **The National Center of Complementary and Alternative Medicine**

Supported by P50AT002776 from the National Center for Complementary and Alternative Medicine (NCCAM) and the Office of Dietary Supplements (ODS) which funds the Botanical Research Center of Pennington Biomedical Research Center and the Department of Plant Biology and Pathology in the School of Environmental and Biological Sciences (SEBS) of Rutgers University.

### **Study Intervention Provided by:**

The product for the clinical studies will be obtained from the Botanical Core Lab of the Rutgers Component of the Botanical Research Center. Working in collaboration with [name] at the Louisiana State University Food Science department, the final product will be delivered to the Pennington Biomedical Research Center where the clinical study will be performed. Specifically, *Artemisia dracunculus* herb was grown from seed by ARC Greenhouses in cooperation with Rutgers University.

### **Sponsor of IND (IDE):**

No IND is required for this study, see attached letter (Appendix A)

## Tool Revision History

Version Number: Version 4

Version Date: January 20, 2014

Summary of Revisions Made: Have revised Figure 1 to add a ten and 22 hour time point corresponding to "hour of OGTT". Have added a new Table 2 to provide clarification of time points and blood draws of bioactives in relations to OGTT blood draws

Version Number: 4.0 Version Date: 05Oct2016

Summary of Revisions Made: Dosing of MAD phase will be done overlapping as opposed to consecutively. The change is suggested based on safety profile observed for the SAD study utilizing all doses proposed in the current proposal

Version Number: Version Date:

Summary of Revisions Made:

Version Number: Version Date:

Summary of Revisions Made:

## PRÉCIS

### Study Title

Evaluation of soy-protein isolate Russian tarragon (*Artemisia dracunculus* L.) complex as a dietary supplement to improve carbohydrate metabolism: Dosing, safety and tolerability

### Objectives

The primary objective of this study is to evaluate the effect of nutritional supplementation with a well characterized preparation of *Artemisia dracunculus* L. on safety and tolerability of the preparation. Secondary objectives will evaluate the metabolism of the preparation by assessing the appearance of bioactive compounds in the plasma.

### Design and Outcomes

We will employ 3-treatment crossover designs in which each subject will receive a sequence of 3 mono treatments with washout periods between distinct treatments (extract doses). We will use ascending single oral dose evaluation in a randomized controlled trial and multiple oral dose evaluation in an additional randomized controlled trial to investigate extract safety and tolerability in healthy lean subjects and in healthy subjects who are non-diabetic but with obesity. We will assess safety in the form of biochemical assessments, collection of data on clinical adverse events and will assess plasma appearance of proposed bioactive compounds.

### Interventions and Duration

A soy-protein isolate Russian tarragon (*Artemisia dracunculus* L.) complex will be used as the specific intervention. Dosing for the single ascending dose will be based on preclinical data and on referenced formulas that have been used to scale doses from mice to man or vice versa.

### Sample Size and Population

For the safety and tolerability studies, healthy subjects who have passed all screening evaluations and have given informed consent will be recruited. Approximately 27 subjects (3 cohorts of 9 subjects) will participate in the single dose studies. For the multiple dose studies, we plan to enroll an additional 27 participants (3 cohorts of 9 subjects). In the single dose studies, participants will be healthy adults with BMI 18.5 – 32 kg/m^2. In the multiple dose studies, participants will be stratified by body mass index (BMI) so that 1 normal weight (BMI < 25), 1 overweight (BMI 25-29) and 1 obese (BMI 30+) participant will be in each treatment sequence. Observers will be blinded to treatment sequence for each participant until the database has been locked.

## 1. STUDY OBJECTIVES

### 1.1 Primary Objectives

#### Phase 1 Studies: Ascending Single Oral Dose Evaluation

The **Primary objective** will be to assess the safety and tolerability of a single dose of the soy-protein isolate Russian tarragon (*Artemisia dracunculus* L.) complex in healthy lean subjects.

Although this study is not designed to evaluate efficacy, we will assess the effect of a single dose of the botanical complex on glucose tolerance to determine if there is an acute effect.

### **Phase 1 Studies: Multiple Oral Dose Evaluation**

A **Primary objective** is to assess the safety and tolerability of multiple daily doses of the soy-protein isolate Russian tarragon (*Artemisia dracunculus* L.) complex in healthy lean subjects and in healthy subjects who are considered overweight or obese.

#### **1.2 Secondary Objectives**

A **secondary objective** is to assess the metabolism of the preparation by assessing plasma appearance of proposed bioactives after dosing.

A **secondary objective** is to assess possible mechanism of action operative *in vivo* for the soy-protein isolate Russian tarragon (*Artemisia dracunculus* L.) complex by determining effect on insulin secretion and/or effects on lipid profiles.

## **2. BACKGROUND AND RATIONALE**

### **2.1 Background on Condition, Disease, or Other Primary Study Focus**

It is well known that Type 2 diabetes is a progressive disorder whose pathophysiology consists of pancreatic dysfunction, hepatic glucose overproduction and insulin resistance in peripheral tissues. As such, clinical strategies to achieve glycemic control endorse the use of a combination of agents from multiple pharmacologic classes and which target specific pathophysiologic defects. In particular, the enhancement of insulin sensitivity remains as a primary clinical strategy given the role of insulin resistance in the pathophysiology of type 2 diabetes. Recent data, however, have questioned the safety of the current pharmacologic agents used to enhance insulin sensitivity. As such, alternative strategies, e.g., nutritional supplementation with over-the-counter agents, are extensively practiced by a large number of patients and are frequently done so without the knowledge of the provider. Based on historical human use, there has been great interest in plant extracts (botanicals) as a source for nutritional supplements intended as adjunctive therapies for human diseases. Specifically, isolated compounds identified from plant sources, i.e. phytochemicals or bioactives, have served as a source for therapeutic agents for many diseases, including malignancy, infectious diseases and diabetes. Interestingly, the development of one of the most commonly used anti-hyperglycemic agents in the world today, i.e. metformin, can be traced to the traditional use of *Galega officinalis* to treat diabetes, and the subsequent search to identify active compounds with reduced toxicity. However, the concern with most nutritional supplements, including those considered "natural" (e.g. botanicals) by the consumer, is the paucity of data in humans in regard to efficacy to improve metabolic abnormalities. Thus, there remains considerable controversy regarding the use of botanical supplements for human health.

Despite the stated concerns for botanical supplements, many botanicals have shown considerable promise for human use. In particular, plants from the genus *Artemisia*, and

specifically *Artemisia dracunculus* L. (Russian tarragon) have a long history of medicinal and culinary use and have been reported to have efficacy as a traditional treatment for diabetes in various parts of the world. Specifically, the ethanolic extract of *A. dracunculus* L. significantly decreased blood glucose levels and improved insulin levels in both genetic and chemically induced murine models. As a proposed mechanism of action, enhanced insulin receptor signaling was demonstrated in primary human skeletal muscle culture exposed to specific concentrations of the *A. dracunculus* L. extract. In addition, at least 5 bioactive compounds have been identified in *A. dracunculus* L. that have specific effects *in vitro* on mechanisms contributing to gluco-regulation. Yet, despite the promising *in vitro* studies, clinical efficacy data for the extract in carefully controlled clinical research studies are lacking. Thus, the overall objective of this study is to conduct early human investigation and to evaluate the effect of nutritional supplementation with a well characterized extract of *Artemisia dracunculus* L. The primary objectives would be to evaluate safety, tolerability and effective dose in non-diabetic human subjects. Secondary objectives would assess metabolism of the extract and evaluate effects on proposed mechanisms such as insulin secretion, lipid levels and/or insulin resistance.

## 2.2 Study Rationale

Our pre-clinical studies have confirmed the potential of *Artemisia dracunculus* L. to be developed as an effective nutritional supplement to address components of metabolic syndrome. The completed studies as proposed will provide the necessary data for large scale Phase III randomized clinical intervention trials.

**Experiments Proposed.** Studies will assess the effect of a soy-protein isolate Russian tarragon (*Artemisia dracunculus* L.) complex (termed 5011-Nutrasorb®) as a dietary supplement to improve carbohydrate metabolism. Protocols will be designed to evaluate feasibility, dose range effects, pharmacology, safety and biological efficacy of the botanical complex. We submitted an application for review to the FDA and were informed that “*use of this product in the manner described in the information you submitted does not require an IND*”. The soy-protein isolate Russian tarragon complex will primarily be tested in this application with use of ascending single and multiple oral dose Phase 1 studies.

**Source and Preparation:** As outlined, PMI-5011 is an ethanolic extract of *Artemisia dracunculus* L., also known as Russian tarragon. The plant has been used as a medicinal botanical or food for centuries and continues to be cultivated in Europe. PMI-5011 has been the primary study focus of our NIH Botanical Research Center since 2005 and a study focus at Rutgers University for at least 10 additional years. Extensive safety testing has been conducted with the botanical extract including complete Ames analysis, a 14-day repeated-dose oral toxicity study in rats and an oral subchronic 90-day toxicity study in rats, none of which showed any indication of toxicity. Based on these studies, it was felt that PMI-5011 would be an attractive dietary supplement for human use in the area of improving glucose metabolism.

In the proposed clinical study, we will use an alternative preparation of *Artemisia dracunculus* L. Rather than extracting the herb with 60% ethanol and drying the extract into a sticky paste-like residue, we propose to make a hot water tea-like extract which will be mixed with soy protein

isolate, a common component of many foods. The polyphenols that have been identified as bioactive from the ethanolic extract will bind to the soy protein isolate, which can then be separated from the water and dried. This process has been used successfully to concentrate polyphenols from green tea and anthocyanins from sugary berry juices. Since the basic process involves the mixing of two foods and removal of water, it is equivalent to cooking. The resulting product remains a food, and we feel it can be Generally Regarded as Safe (GRAS). In addition to eliminating the need for organic solvent (ethanol) use and disposal, this process removes chlorophyll and other non-polar compounds which are retained when ethanol is used as an organic solvent for *Artemisia dracunculus* and which tend to make the extract insoluble and less bioavailable. Polyphenol concentrations in the soy protein mixture are comparable to those in the ethanol extract. 5011-Nutrasorb is not intended to cure, prevent or mitigate a disease. Its suggested use is to maintain normal functions of the human body. Because it is made by simple mixing and separating of two foods (Russian tarragon tea and soy protein), we believe that the resulting substance can be Generally Regarded as Safe (GRAS).

### 3. STUDY DESIGN

#### A. Phase 1 Studies: Ascending Single Oral Dose Evaluation

**Objective:** The **primary objective** will be to assess the safety and tolerability of a single dose of the 5011-Nutrasorb in healthy subjects. Although this study is not designed to evaluate efficacy, we will assess the effect of a single dose of the botanical complex on glucose tolerance to determine if there is an acute effect.

**Subjects:** Twenty seven healthy subjects (3 cohorts of 9 subjects) who have passed all screening evaluations and have given informed consent will be recruited for the Phase I studies. Healthy subjects are defined as individuals who are free of significant cardiac, pulmonary, gastrointestinal, hepatic, renal, hematological, endocrine, neurological and psychiatric disease as determined by history, physical examination and clinical laboratory tests.

**Dosing:** A representative dosing schedule and randomization for this study is outlined in Table 1. We will begin dosing at very low doses based on the dose response data generated from the mice studies. Based on dosing considerations (see Section 5.1), the suggested dosing range would be 3-30 g subject. Thus, our suggested doses will be 0.3, 1, 3, 10, 20 and 30 g. We will use the same extract dose for all participants irrespective of their weight. Each subject will receive three single doses (two doses of 5011-Nutrasorb and one of placebo) separated by washout periods of at least 7 days. In each treatment period a single dose of extract will be administered on day 1. Up to 9 treatment sequences (3 sequences in each of 3 cohorts) are planned for the single dose evaluations (**Table 1**).

Table 1. Ascending Oral Dose Randomization			
	Period 1	Period 2	Period 3
COHORT 1			
Sequence 1 (n=3)	Dose 1	Dose 2	Placebo
Sequence 2 (n=3)	Dose 1	Placebo	Dose 2
Sequence 3 (n=3)	Placebo	Dose 1	Dose 2
COHORT 2			
Sequence 4 (n=3)	Dose 3	Dose 4	Placebo
Sequence 5 (n=3)	Dose 3	Placebo	Dose 4
Sequence 6 (n=3)	Placebo	Dose 3	Dose 4
COHORT 3			
Sequence 7 (n=3)	Dose 5	Dose 6	Placebo
Sequence 8 (n=3)	Dose 5	Placebo	Dose 6
Sequence 9 (n=3)	Placebo	Dose 5	Dose 6

Complete blood chemistry will be obtained prior to and after dosing. After dosing, glucose tolerance studies are conducted. As part of the glucose tolerance, both glucose and insulin will be obtained at baseline, and at 30, 60, 90, 120, and 180 minutes after dosing. Plasma will also be stored and archived for later analysis of proposed bioactive compounds.

Before the next cohort is commenced, subjects in the previous cohort must have received all 3 treatments and the safety and tolerability data assessed and show good tolerability and the following information must be available in a safety summary provided by the investigator: (1) adverse events, (2) complete hematologic and biochemistry profile in blood, (3) measures of glucose and insulin response to glucose tolerance. Statistical analyses will be conducted to assess whether there is residual effect of extract after washout.

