### Assessments and Evaluations:

*Baseline/Screening Evaluation:* For the single dose study, all subjects will undergo an outpatient screening evaluation to assess their eligibility prior to entrance into the study. A complete medical history and physical examination will be performed. Blood samples will be taken for a complete blood chemistry, blood counts, thyroid hormone panel and urinalysis. Subjects with impaired glucose tolerance or diabetes will be excluded. During baseline, subjects will be assessed for dietary intake data and instructed on weight maintenance diets. A taste (small sip) of the study product (30g) will also be administered during screening.

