### Study Design of Ascending Single Dose

**Objective:** The Primary objective will be to assess the safety and tolerability of a single dose of the 5011-Nutrasorb in healthy subjects. Although this study is not designed to evaluate efficacy, we will assess the effect of a single dose of the botanical complex on glucose tolerance to determine if there is an acute effect.

**Design:** After all inclusion and exclusion criteria are met, subjects will be admitted to the inpatient unit of the Pennington Biomedical Research Center. After meeting inclusion and exclusion criteria, they will be randomized by the study statistician to receive a specific sequence of 3 treatments (3 doses of extract). Participants will be randomly assigned to

treatment sequences as this design balances order of treatment consumption with respect to the distribution of extraneous factors, known or unknown, that may potentially confound the association and assessment of botanical supplement use and carbohydrate metabolism. After baseline evaluation, subjects within each cohort will be randomized to one of 3 treatment sequences (order of receiving 2 doses of 5011-Nutrasorb and placebo based on the dosing plan outlined in **Table 1**). The statistician will prepare and give to the pharmacist a randomization schedule that is divided into 3 parts, one for each cohort. Nine treatment sequences will be indicated for each cohort in 3 permuted blocks of 3 treatment sequences where each treatment sequence appears exactly once in permuted block. This balances the use of treatment sequences throughout the duration of participants in the event that anticipated dose usage requires adjusting before completion of all treatment sequence assignments.

Figure 1: Single Ascending Dose Study														
Day of Study	Scr	-3	1	1	1	1	1	1	1	1	1	1	2	2
Hour of OGTT			-2	-1.5	-1	-0.5	0	1	2	4	10	12	22	24
Randomization			•											
Dosing	taste		•											
Vital Signs	•	•	•					•		•		•		•
Body Weight	•													•
Complete Blood Chemistry	•													•
Physical Exam	•													•
EKG	•									•				
OGTT a		•					•							
Adverse Event Assessment						•	•	•						•
Fasting Lipids	•													•
Insulin/Glucose b	•											•		•
Bioactives: Plasma		•	•	•	•	•	•	•	•	•	•			•

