**Dosing:** Twenty Seven subjects (3 cohorts of 9 subjects with 3 subjects (1 normal weight, 1 overweight and 1 obese) randomly assigned to each of 3 treatment sequences) will participate in a three period crossover treatment regimen with each treatment period comprising once daily dosing for 21 days. Subjects will be randomly assigned to receive the treatments in the sequence orders shown in **Table 2**: 1) Cohort 1 will comprise 3 sequences of 3 treatments where placebo is dose 0 of 5011-Nutrasorb, D1 is a low dose (0.3 g) of 5011-Nutrasorb and D2 a medium dose (1 g) of 5011-Nutrasorb; 2) Cohort 2 will comprise 3 sequences of 3 treatments where D2 is a medium dose (1 g) of the 5011-Nutrasorb and D3 (30 g) a high dose of the 5011-Nutrasorb; and 3) Cohort 3 will comprise 3 sequences of 3 treatments where D1 is a low dose (0.3 g) of the 5011- Nutrasorb and D3 a high dose (30 g) of the 5011-Nutrasorb. Dosing for the MAD study was determined by data obtained in the SAD study as outlined above. Specifically, as outlined in Table 1, we will have data on PK studies, safety and tolerability, and biological response. In addition, based on information from the plasma appearance data and from assessment of biological response, consideration will be given to providing dosing on a BID or TID regimen. All doses used in this phase have been tested in the single-dose portion of the protocol. In the single dose protocol, there was no observed signal for toxicity, tolerability or other adverse events noted. The doses evaluated in the single dose study are spread among all 3 cohorts and no new dose is being introduced in this phase. Blinded analysis of the glucose tolerance will be on-going during the study and dose changes will be made if necessary. Additionally, as stated, if none of these doses show adequate glucose tolerance effects then an additional cohort may be added to investigate a twice daily or three times a day dose. In each treatment period a single dose of the 5011- Nutrasorb will be administered daily

from days 1 to 21. Complete biochemical and hematologic assessments to evaluate safety will be obtained in addition to clinical monitoring for adverse events.

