### **7.3 Adverse Events and Serious Adverse Events**

An AE is any untoward medical occurrence in a patient or clinical investigation subject, temporally associated with the use of a medicinal product, whether or not considered related to the medicinal product. We define AE as any unfavorable and unintended sign (including an abnormal laboratory finding), symptom, or disease (new or exacerbated) temporally associated with the use of a medicinal product.

Events meeting the definition of an AE include:

- Any abnormal laboratory test results (hematology, clinical chemistry, or urinalysis) or other safety assessments (e.g., ECGs, radiological scans, vital signs measurements), including those that worsen from baseline, and felt to be clinically significant in the medical and scientific judgment of the investigator.
- Exacerbation of a chronic or intermittent pre-existing condition including either an increase in frequency and/or intensity of the condition.
- New conditions detected or diagnosed after study treatment administration even though it may have been present prior to the start of the study.
- Signs, symptoms, or the clinical sequelae of a suspected interaction.
- Signs, symptoms, or the clinical sequelae of a suspected overdose of either study treatment or a concomitant medication (overdose per se will not be reported as an AE/SAE).

Events that do not meet the definition of an AE include:

- Any clinically significant abnormal laboratory findings or other abnormal safety assessments that are associated with the underlying disease, unless judged by the investigator to be more severe than expected for the subject's condition.
- The disease/disorder being studied, or expected progression, signs, or symptoms of the disease/disorder being studied, unless more severe than expected for the subject's condition.
- Medical or surgical procedure (e.g., endoscopy, appendectomy); the condition that leads to the procedure is an AE.
- Situations where an untoward medical occurrence did not occur (social and/or convenience admission to a hospital).
- Anticipated day-to-day fluctuations of pre-existing disease(s) or condition(s) present or detected at the start of the study that do not worsen.

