### 9.2 Sample Size and Randomization

As comparative efficacy of the extracts is not the primary issue in this protocol, power to detect efficacious effects is not specifically evaluated to justify sample sizes. A sample of 27 subjects (3 subjects in each of 3 treatment sequences in each of 3 cohorts) will be enrolled in the ascending single dose evaluation. Thus, all 9 subjects in Cohort 1 will receive the placebo and both dose 1 and dose 2 of the extract; similarly all 9 subjects in Cohort 2 will receive the placebo and both dose 3 and dose 4 of the extract; and all 9 subjects in Cohort 3 will receive the placebo and both dose 5 and dose 6 of the extract. Before the next cohort is commenced, subjects in the preceding cohort must have received all 3 treatments and the safety and tolerability data must have been assessed showing good tolerability; and information must be available in a safety summary of adverse events, complete hematologic and biochemistry profile in blood, and measures of glucose and insulin response to glucose tolerance.

The 9 subjects in each cohort for the SAD study will be enrolled with 3 subjects in each of 3 strata (normal weight – BMI =18.5-24.9 kg/m^2; overweight -- BMI = 25.0-29.9 kg/m^2; obese – BMI = 30.0-32 kg/m^2). The randomization will be carried out within each weight stratum so that one normal weight, one overweight, and one obese subject will be assigned to each sequence.

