#### **9.6 Data Analyses**

Statistical comparisons will focus on comparisons between subjects randomized to the selected *Artemisia* sp. extract and the placebo group with respect to baseline to follow-up change in: (a) a descriptive summary of adverse events, complete hematologic and biochemistry profile in blood, and measures of glucose and insulin response to glucose tolerance will be compiled for both single and multiple dose studies; (b) measurements assessing lipid metabolism, i.e. fasting lipid profile; (c) physiologic assessments of insulin action (HOMA-IR) and insulin secretion; and (d) body weight/body composition. For each outcome, the equality of the outcome means for 5011-Nutrasorb versus placebo will be tested against a two-directional alternative, controlling the type 1 error at  $\alpha = 0.05$ . The analyses will be conducted using mixed effects linear statistical

models with repeated measures to conduct analysis of variance for crossover designs. Post-hoc tests will be conducted for pairwise comparisons of extract doses and placebo employing the Tukey method for controlling the global comparison-wise significance at 0.05 level. Logarithms or other transformations will be analyzed for data seriously deviating from normality; alternatively, non-parametric analyses may be conducted.

Handling of missing data: The data will be analyzed using the procedures PROC MIXED and PROC GLIMMIX SAS (v 9.3 or later). Thus, mixed effects models for repeated measures will be employed to analyze all available data irrespective of missing or incomplete data attributable to dropouts or other phenomena. Our experience in previous studies that employed similar study designs resulted in little if any missing data. Nevertheless, in anticipation of the possibility of such we plan to conduct sensitivity analyses that compare our findings against protocol completer analyses and last observation carried forward analyses in addition to investigating characteristics of participants who fail to protocol.

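### The single-dose escalation condition and the Section 9.6 safety summary require haematology, but Figures 1 and 2 schedule only blood chemistry after dosing

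*Combined protocol and SAP*

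**What the plan says.** **What is required.** Section 3.A lists what must be in the investigator's safety summary before the next single-dose cohort starts. Item "2) complete hematologic and biochemistry profile in blood" stands between adverse events and the glucose and insulin response. Section 9.2 repeats the condition: "information must be available in a safety summary of adverse events, complete hematologic and biochemistry profile in blood". Section 9.6 plans "a descriptive summary of adverse events, complete hematologic and biochemistry profile in blood" for both studies, under an opening phrase about change from baseline to follow-up. For the multiple-dose study, the Dosing paragraph of Section 3.B says "Complete biochemical and hematologic assessments to evaluate safety will be" obtained, without naming days.

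**What is scheduled.** Sections 6, 6.1, 6.2.4 and 6.2.5 refer the reader to Figures 1 and 2. The only general safety-laboratory row in either figure is "Complete Blood Chemistry". Figure 1 marks it at screening and on Day 2 (hour 24). Figure 2 marks it at screening and on Days 7, 14 and 21. The single-dose text in Section 3.A also names chemistry alone as the test before and after dosing. The design paragraph of Section 3.B places repeat safety labs on Days 7, 14 and 21 but does not say what they contain.

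**How the terms are used.** At screening, in both studies: "Blood samples will be taken for a complete blood chemistry, blood counts, thyroid hormone panel and urinalysis". Blood counts and chemistry are listed there as different tests.

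**The concern.** Safety and tolerability, judged clinically and biochemically, are the primary outcome (Section 9.5.1), and Section 9.1 describes these trials as the first human testing of the extract. If staff order what the figures list, the single-dose escalation decision is taken without one of the results that Sections 3.A and 9.2 say must be available. The haematology part of the 9.6 summary then has a screening value and no follow-up value.

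The consequence carries forward. Section 3.B relies on the absence of a toxicity signal in the single-dose study when it describes the multiple-dose regimen, and the revision history gives the single-dose safety profile as the reason for overlapping rather than consecutive dosing. If post-dose counts were not drawn, that statement does not cover haematology. The multiple-dose study then exposes each subject for 21 days per period.

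**Working it through.** The plan states no figure on this point, so there is none to reproduce. The check is a cross-reading followed by a count.

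**Step 1. Does the chemistry row include blood counts?** On the protocol's own usage, no. The screening text in Sections 3.A, 3.B and 6.2.2 lists chemistry and blood counts as separate items. Sections 3.A, 9.2 and 9.6 likewise pair a haematologic with a biochemistry component.

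**Step 2. Does any text supply a post-dose count that the figures omit?**
- Single dose: the post-dose sentence in Section 3.A names chemistry, and Figure 1 agrees. The specific methods in Section 6.2 cover glucose tolerance, insulin indices, lipids, body composition and bioactives, not blood counts. The only support is indirect: the escalation condition presupposes that a result exists.
- Multiple dose: yes, in part. The Dosing paragraph commits to haematologic assessments but gives no days. The design paragraph gives days for safety labs but no contents. Figure 2 gives days and names chemistry only.

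**Step 3. Count the marked post-dose laboratory points.**
- Subjects per study: 3 cohorts × 3 sequences × 3 subjects = 27.
- Single dose: 27 subjects × 3 periods × 1 marked day = 81, of which 27 × 2 = 54 follow extract and 27 follow placebo.
- Multiple dose: 27 × 3 periods × 3 marked days = 243, of which 27 × 2 × 3 = 162 are on extract and 27 × 3 = 81 on placebo.
- Points at which a blood count is itemised: 0 of 81 and 0 of 243.

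**Step 4. What would counts at those points show?** Each single dose is given to 9 subjects. Each multiple dose appears in two of the three cohorts, so 18 subjects receive it. The chance of at least one subject with an abnormal count at a given dose is 1 − (1 − p)^n. The documents give no rate p, so the rates below are assumptions.

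| Assumed p | n = 9 (single dose) | n = 18 (multiple dose) |
|---|---|---|
| 5% | 37% | 60% |
| 10% | 61% | 85% |
| 20% | 87% | 98% |
| 30% | 96% | 99.8% |

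Even with counts at every marked visit, a 5% effect would more often than not go unseen at any one single dose. At 20% or more, the counts would usually reveal it.

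**The case against.** The strongest reply is that the figures are not complete lists of tests. They omit the blood counts, thyroid panel and urinalysis that the text requires at screening. Figure 1 omits the 6-hour urine collection described in Section 3.A, and neither figure shows the pregnancy test required by Section 4.2. A missing row therefore does not prove a missing sample, and the chemistry row may be shorthand for a fuller panel. This stands as a limit on what can be concluded. It does not remove the mismatch: at screening the text supplies the omitted tests, whereas after a single dose the text also names chemistry alone.

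For the multiple-dose study the reply is stronger. Section 3.B does commit to haematology and gives days for safety labs, so the defect there is undefined content and timing, not a missing commitment.

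A reader might infer more than the documents support:
- *That escalation cannot proceed.* The condition itself instructs that a haematologic profile be available, and staff may draw unscheduled counts. Section 3.B also treats single-dose testing as done up to 30 g, which is Dose 6 and is given only in Cohort 3, so both escalation steps had been passed.
- *That a whole item of the safety summary is absent, or that both studies have this condition.* The biochemistry half of the item is scheduled, and the cohort condition applies to the single-dose study only.
- *That haematological toxicity could not be detected.* Section 7.3 gives "Any abnormal laboratory test results (hematology, clinical chemistry, or urinalysis) or other safety assessments" as examples of what can be an adverse event and does not depend on a scheduled test. Section 7.5 allows extra laboratory tests, and Section 8 requires safety labs at withdrawal.
- *That post-dose urinalysis is also owed.* The required profile is in blood, and Section 3.B promises only biochemical and haematologic assessments.

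**Conclusion.** The inconsistency is real and should be corrected. Haematology is required for single-dose escalation and for the 9.6 summary of both studies, yet no row or dated procedure itemises a post-dose blood count at any of the 81 single-dose or 243 multiple-dose laboratory points. The haematology half of the second item in the safety summary, and the haematology part of the 9.6 summary, therefore depend on unscheduled or unspecified draws. The gap is wider in the single-dose study, where text and figure agree on chemistry alone, than in the multiple-dose study, where the commitment exists but is not carried into Figure 2.

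The documents do not establish that counts were not drawn, that the escalation condition was unmeetable, or that haematological toxicity was invisible. The conclusion assumes that the chemistry row means what the screening text implies, that the schedule marks fall in the columns as read, and that the image beside the Section 3.B screening text, which could not be read, adds no further laboratory schedule.

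**What to change.** 1. In Figures 1 and 2, add blood counts to the chemistry row at the visits already marked: screening and Day 2 in Figure 1; screening and Days 7, 14 and 21 in Figure 2.
2. Define the complete blood chemistry and the safety labs once, by listing their contents, and use those definitions in Sections 3.A, 3.B, 9.2 and 9.6.
3. For single-dose cohorts already completed, state whether post-dose counts were obtained. If they were, report them in the 9.6 summary. If not, limit the Section 3.B statement about the absence of a toxicity signal to the tests that were done.

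Added at the marked visits, this yields up to 81 single-dose and 243 multiple-dose post-dose counts. For cohorts already completed the Figure 1 change has no prospective effect, and step 3 does the work. The cost is one extra small tube and the assay at venepunctures already planned, plus an amendment to two tables. No new visit is needed.
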